3.3 Summary of known and potential risks and benefits

There is substantial evidence that supplementation with the precursor of Impryl®, named Condensyl®, is safe and of beneficial in case of absolute (low content in the diet) or relative (increased demand) deficiency.(17) These deficiencies may associate to altered homocysteine metabolism and other disturbances to the defense against oxidative aggressions and are often observed in men and women with reproductive problems. It is to be noted that disturbances of homocysteine metabolism and of oxidative defenses may occur more frequently in subjects carrying a defective genetic variant of one of the main enzymes of homocysteine metabolism including those denominated ethyltetrahydrofolate reductase (MTHFR), methionine transferase reductase (MTRR), Betaine Homocysteine Methyl Transferase (BHMT) and cystathionine beta synthase (CBS).(13) Impryl® has been formulated so to compensate these defects by providing an already activated

substrate (i.e. methylfolate for MTHFR and methyl cobalamin for MTRR), or by providing an excess of substrate (i.e. betaine for BHMT) or by delivering a ready substrate for downstream to the genetic blockade (i.e. cystine for CBS). Thus, Impryl® will deliver an effective dietary support to everybody independently of their genetic substrate for the mentioned enzymes.

Impryl is safe by administering only essential micronutrients that are usually occurring in food, supplied according the recommended daily dose. There are no major warning, there are no reports on side effects or allergies, it is gluten- and lactose free.

3.4 Description and justification of route of administration and dosage

The route of administration of both Impryl® and placebo is by oral intake with a small amount of water, preferentially without food. The recommended daily dose is 1 tablet per day. The assumption of a smaller amount does not guarantee full coverage of the daily need in all subjects. The recommended daily dose should not be exceeded.

3.5 Dosages, dosage modifications and method of administration

All subjects will receive the same dosage of 1 tablet (1.3 gram) taken between meals once a day. No dosage modifications are possible. The medication will be taken orally.

3.6 Preparation and labelling of Investigational Medicinal Product

Manufacturing, preparation, labelling and packaging of both the active verum (Impryl®) and placebo tablets will be performed by Labomar SRL compliant with EU GMP. The labels will be in Dutch. A flaglabel (to be teared off) is used to identify placebo and Impryl®. Distribution of study medication will be organised by either the Radboudumc, department of Reproductive Medicine, or at the local department of Gynaecology at every site. Every centre was given the option to perform randomisation and distribute the study medication at their own hospital or asking their included patients to collect study medication after randomisation at Radboudumc at the above mentioned department.

3.7 Drug storage accountability

The coding and distribution to the trial will be organised by Labomar SRL in collaboration with the principal and coordinating investigators of the Radboudumc. The study medication has to be stored in a dry place at room temperature. No special precautions have to be taken into account. Patients are not asked to return study medication. Since it is a supplement and not medication there are no special precautions for destruction or disposal.

Drug accountability will be performed in line with GCP requirements. The investigator is responsible for drug accountability and these tasks will be delegated to the primary investigators at the sites. We will log all dispensing of the investigational product on a drug

accountability log . See paragraph 5.2 of this protocol for further details on the dispensing and logging.

4. NON-INVESTIGATIONAL PRODUCT

Not applicable

5. METHODS

5.1 Study parameters/endpoints

5.1.1 Main study parameter/endpoint

Number of ongoing pregnancies, conceived in the time window between randomization up to and including month 6 of intervention use. Ongoing pregnancy is defined as a visible embryonic heartbeat at ultrasound from 10-12 weeks of gestation onwards.

5.1.2 Secondary study parameters/endpoints

Number of pregnancies conceived in the optimal intervention time window, i.e. between start of month 4 till the end of month 6.

Overall number of pregnancies meaning the cumulative pregnancy number up to 9 months after start of intervention

Time to pregnancy defined as

- a) the time between start randomization and reaching ongoing pregnancy (confirmed by ultrasound)
- b) the time between start of fertility treatment during the study (EM, IUI, IVF/ICSI) and reaching ongoing pregnancy

Change in semen parameters in IUI/IVF/ICSI group based on pre-wash total motile sperm count (TMSC), leading to different fertility treatment categorisation (EM, IUI, IVF, ICSI), from a subpopulation of patients: Radboudumc patients and patients from other sites having pre-wash TMSC as standard procedure when semen is used for IUI or IVF/ICSI.

Improvement between Impryl® and control group in fertilization rate and embryo-utilization rate in IVF/ICSI group. Fertilization rate is defined as the percentage of oocytes with 0 PN or ≥ 2 PN after insemination (IVF) or injection (ICSI). Abnormal fertilization such as 3PN will be recorded, in case this percentage differs or increases in the study group. The embryo-utilization rate (EUR) is defined as the number of high quality embryos obtained, embryo's used at transfer plus the number of embryos frozen, divided by the number of zygotes obtained in a cycle. Due to the differences in embryo evaluation and embryo selection criteria for cryopreservation, we decided to measure the relative increase in fertilization and utilization rate observed for each clinic.

Number of miscarriages (defined as non-vital intra-uterine pregnancy before 16 weeks of gestation)

Live birth rate (beyond 24 weeks, defined as the birth of a living child) within study-period of 15 months

Adverse effects

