Number of pregnancies conceived in the optimal intervention time window, i.e. between start of month 4 till the end of month 6. Overall pregnancy rate. Time to pregnancy defined as both the time between a) randomization and reaching ongoing pregnancy, and as b) start of fertility treatment during the study (EM, IUI, IVF/ICSI) and reaching ongoing pregnancy. Change in semen parameters leading to different fertility treatment categorisation (for more details see page 26) between baseline and 3 months intervention, based on pre-wash total motile sperm count (TMSC) from the subpopulation from Radboudumc and sites that deliver a pre-wash TMSC before IUI/IVF/ICSI. Improvement between Impryl® and control group in fertilization rate and embryo-utilization rate in IVF/ICSI group. Fertilization rate is defined as the percentage of oocytes with 0 PN or ≥ 2 PN after insemination (IVF) or injection (ICSI). Abnormal fertilization such as 3PN will be recorded, in case this percentage differs or increases in the study group. The embryo-utilization rate (EUR) is defined as the number of high quality embryos obtained, embryo's used at transfer plus the number of embryos frozen, divided by the number of zygotes obtained in a cycle. Due to the differences in embryo evaluation and embryo selection criteria for cryopreservation, we decided to measure the relative increase in fertilization and utilization rate observed for each clinic.. Number of miscarriages defined as a non-vital intra-uterine pregnancy before 16 weeks of gestation. Live birth rate defined as beyond 24 weeks of gestation, the birth of a living child. Live births (beyond 24 weeks, defined as the birth of a living child) will be reported within follow-up time of 15 months. Furthermore the following adverse events will be reported: gastro-intestinal problems such as reflux, obstipation, diarrhea, nausea or vomiting, furthermore loss of appetite, headache, dizziness, pruritus or skin rash.

STUDY DESIGN

A multicentre randomised, double blind placebo controlled, clinical trial for Impryl® administration will be performed in the Department of Gynaecology and/or Reproductive Medicine in both academic and non-academic hospitals in The Netherlands.

The 16 centers participating in the study:

| Hospital | Principal investigator |
|---|--------------------------------|
| Radboudumc, Nijmegen | [name] |
| Slingeland Ziekenhuis, Doetinchem | [name] |

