The ratio between the 3 fertility treatment groups (EM 1: IUI 3: IVF/ICSI 2) is based on the number of new patients treated at Radboudumc and the sites each year. To test the effect of Impryl on the probability of ongoing pregnancy, a sample size of 600 men per treatment group (1200 in total) is needed, assuming differences in ongoing pregnancy rates of 6.5% and an expected ongoing pregnancy rate of 20% in the placebo group, with a two-sided alpha of 5% and a beta of 24% (i.e. 76% power). As we expect the number of participants lost to follow up to be minimal. We will allocate 600 patients in both intervention and control arm. Figure 1 shows the distribution of the number of participants for the 3 different types of fertility treatment (EM, IUI and IVF/ICSI).

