Semen analysis will be performed two times: once during diagnostic work-up (standard care, analysis according to WHO criteria(28) and once more after approximately 3 months of using study medication (ie. after three months of IUI treatment or IVF/ICSI). At several sites, a pre-wash TMSC is standard care when performing an insemination (IUI group) and will be performed on the semen produced for IVF/ICSI as part of routine measurement before procedure. Because semen analysis performed at the time of treatment cannot be fully performed according to the WHO criteria, we will categorize the TMSC quality according to the allocated treatment category. This means, that the TMSC (evaluated at the start of treatment and after 3 months) will be analyzed according to changes in allocated treatment category based on the NVOG guideline(29). The criteria for treatment are given in the table below. A change in treatment category means an improvement in sperm quality that would allow a lower treatment category (e.g, from ICSI to IVF)

| TMSC outcome ($\times 10^6$) | WHO Diagnostic category | NVOG Treatment category |
|--------------------------------|-------------------------|---|
| > 10 | Normospermia | EM |
| 3 -10 | Mild OAT | IUI |
| 1-3 | OAT | IVF/ICSI (if after wash VCM is <0,5) |
| <1 | Extreme OAT/Azoospermia | ICSI |

OAT = oligo-astheno-teratozoospermia.

* Or IVF depending on the prediction model of Hunault and other clinical characteristics

We decided not to perform a semen analysis in the EM group due to the fact that they already have normal semen parameters at intake and the burden of an extra visit is high.

Fertilization and embryo-utilization rate

In IVF/ICSI patients fertilization rate and embryo-utilization rate are standard reported by every IVF-laboratory. Fertilization rate is the percentage of oocytes with ≥ 2 PN after insemination (IVF) or injection (ICSI). The embryo-utilization rate (EUR) is defined as the number of high quality embryos obtained, embryo's used at transfer plus the number of embryos frozen, divided by the number of zygotes obtained in a cycle. Due to the differences in embryo evaluation and embryo selection criteria for cryopreservation, we decided to measure the relative increase in fertilization and utilization rate observed for each clinic.

Transvaginal ultrasonography

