7. STATISTICAL ANALYSIS

All data will be analyzed on an intention-to-treat basis. Data of patients who are lost to follow-up, will be included in their randomised group

will be included in their randomized group:

- Patients who are lost to follow-up during the treatment period are considered not to have achieved a pregnancy.
- Patients, who are lost to follow-up right after achieving a pregnancy of less than 8 weeks of gestation, are considered not to have achieved an ongoing pregnancy
- Patients, who are lost to follow-up right after achieving a pregnancy of 8 or more weeks of gestation, are considered to have achieved an ongoing pregnancy.

In addition, a per-protocol analysis will be performed for the primary outcome and the secondary outcomes overall pregnancy number, time to pregnancy, number of miscarriages and live birth rate.

Descriptive statistics will be calculated to check for major dissimilarities between study groups with respect to baseline information. Baseline data will be described quantitatively. For continuous variables, we will examine the distribution of the observations, and if normally distributed we will summarise them as means with standard deviations (SDs). If they are not normally distributed, then medians and inter-quartile ranges (IQRs) will be reported. For dichotomous data, we will provide counts and proportions.

The primary outcome variable 'ongoing pregnancy' will be assessed as follows. The ongoing pregnancy percentages as observed in the trial will be presented for both treatment arms, overall, and separately for the three strata (i.e. EM, IUI, IVF/ICSI). In order to adjust for possible imbalances between the treatment groups, the pregnancy percentages and differences in pregnancy percentages between the experimental and control group, and the corresponding 95% confidence intervals will be estimated using a fixed effects binomial model with an identity link, including intervention, fertility treatment, centre and female age (centered). If this model does not converge, a logit link will be used.

Time to ongoing pregnancy will be evaluated by the Kaplan-Meier approach; differences between the two arms will be tested with the log-rank test. Similar analyses will be conducted per stratum (EM, IUI or IVF/ICSI). The other secondary outcomes (overall pregnancy number, number of miscarriages, live birth rate, fertilization rate, embryo-utilization rate) will be evaluated similarly to the primary outcome. Changes in semen

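### Fertilization rate has two conflicting numerators: the Secondary Objectives and 5.1.2 count 0 PN oocytes as successes, 5.3 does not, and section 7 does not choose

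*Combined protocol and SAP*

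**What the plan says.** Three places in the combined protocol and SAP define the fertilization rate, and a fourth uses it.

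- **Objectives, Secondary Objectives:** "Fertilization rate is defined as the percentage of oocytes with 0 PN or ≥ 2 PN".
- **5.1.2 Secondary study parameters/endpoints:** the same numerator, "the percentage of oocytes with 0 PN or ≥ 2 PN after insemination (IVF) or injection (ICSI". The stated aim is "Improvement between Impryl® and control group in fertilization rate and embryo-utilization rate in IVF/ICSI group". This section also says: "Abnormal fertilization such as 3PN will be recorded, in case this percentage differs or increases in the study group".
- **5.3 Study procedures, under fertilization and embryo-utilization rate:** "Fertilization rate is the percentage of oocytes with ≥ 2 PN after insemination (IVF) or injection (ICSI". It adds that every IVF laboratory reports the rate as standard.
- **7. Statistical analysis:** "fertilization rate, embryo-utilization rate) will be evaluated similarly to the primary outcome". It neither defines the rate nor points to 5.1.2 or 5.3.

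The three definitions also say that the effect will be expressed as a relative increase within each clinic. PN is not explained in the list of abbreviations or elsewhere.

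**The concern.** In its ordinary meaning, 0 PN is an oocyte with no pronuclei, that is, without visible fertilization. The two places that define the endpoint put such oocytes in the numerator together with those showing two or more pronuclei. The procedures section leaves them out.

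The endpoint is meant to detect an improvement in fertilization. The most direct improvement is an oocyte that would have stayed at 0 PN reaching ≥2 PN, and under the 5.1.2 wording that oocyte counts as a success both before and after. The same laboratory data can therefore give two different treatment effects, depending on which section the analyst follows. The plan leaves that choice open.

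**Working it through.** The plan gives no expected fertilization rate, power or sample size for this endpoint, so there is no figure of its own to reproduce.

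**Inputs from the documents.** The two numerators are those of 5.1.2 and 5.3. Section 1.3 gives EM : IUI : IVF/ICSI as 1 : 3 : 2, with 600 men per arm and 1200 in total.

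**Assumptions.** The denominator N is all oocytes inseminated or injected. The documents give no distribution over PN classes, so the splits below are illustrative.

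**Step 1, algebra.** Let A be the number of oocytes at 0 PN, B the number at ≥2 PN, and C all others (1 PN and any other class), with A + B + C = N.

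- 5.1.2 rate = (A + B)/N = 1 − C/N
- 5.3 rate = B/N

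Move k oocytes from 0 PN to ≥2 PN:

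- 5.1.2: [(A − k) + (B + k)]/N = (A + B)/N, a change of 0.
- 5.3: (B + k)/N, a change of k/N.

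The zero holds for any PN distribution and for any denominator that the shift does not alter. The 5.1.2 rate responds only to movement into or out of class C.

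**Step 2, partial shifts.** Let g be the gain in ≥2 PN and s the share of it drawn from 0 PN. The 5.3 difference is g and the 5.1.2 difference is g(1 − s). For g = 10 points (assumed):

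| Share s from 0 PN | 5.3 difference | 5.1.2 difference |
|---|---|---|
| 100% | 10 | 0 |
| 75% | 10 | 2.5 |
| 50% | 10 | 5 |
| 25% | 10 | 7.5 |
| 0% | 10 | 10 |

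The part not drawn from 0 PN, g(1 − s), cannot exceed the share of class C. If that class is 5% of oocytes, as assumed in step 3, the 5.1.2 difference is at most 5 points.

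**Step 3, levels and the relative scale.** These are assumed control splits with a 10-point shift wholly from 0 PN:

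| 0 PN / other / ≥2 PN (%) | 5.1.2, control vs active | 5.3, control vs active | 5.3 relative increase |
|---|---|---|---|
| 20 / 5 / 75 | 95 vs 95 | 75 vs 85 | 10/75 = 13% |
| 30 / 5 / 65 | 95 vs 95 | 65 vs 75 | 10/65 = 15% |
| 40 / 5 / 55 | 95 vs 95 | 55 vs 65 | 10/55 = 18% |

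The relative increase under 5.1.2 is 0% in every row. The control-arm level differs between the two definitions by exactly the 0 PN share: 20, 30 or 40 points.

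**Step 4, extreme case.** A cycle with 10 oocytes, all at 0 PN, scores 10/10 = 100% under 5.1.2 and 0/10 = 0% under 5.3.

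**Step 5, reach.** The IVF/ICSI stratum is 1200 × 2/6 = 400 men, or 600 × 2/6 = 200 per arm, as planned.

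**The case against.** The strongest reply is that the faulty wording may never be computed. Section 5.3 says the laboratories report the rate as standard. No section says that 0 PN or 1 PN counts will be collected; only 3 PN is said to be recorded. If each laboratory's own rate is entered, the 0 PN term may drop out unnoticed. This stands as a limit: the harm depends on how the data are captured and which section is followed. It does not remove the conflict, because the plan does not say that the laboratory figure overrides the written endpoint definition.

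A second reply is that the 0 PN term is evidently a slip, copied from one section to the other, and that any embryologist would read past it. A slip is indeed the likely explanation. But the term stands in both places that define the endpoint. An analyst who takes the definition from the endpoint section, as is usual when the analysis section gives none, would apply the problematic numerator.

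Third, the magnitudes are illustrative, and absolute points are not the only scale the plan mentions. Both remarks are fair. Section 7 supports an absolute difference, while the definitions speak of a relative increase; a pure shift from 0 PN to ≥2 PN gives zero on either scale under 5.1.2. The 400 men are a planned stratum size, not the number of couples with an evaluable insemination or injection, which the documents do not give.

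**Conclusion.** The concern holds. The documents give two incompatible numerators for one pre-specified secondary endpoint, and the analysis section does not settle which applies. Followed as written, the 5.1.2 definition does not register a shift from 0 PN to ≥2 PN at all, and it gives a cycle with only 0 PN oocytes a perfect score. For an assumed 10-point gain in ≥2 PN, between 0 and 10 points would appear, depending on where the gain comes from.

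The textual conflict and the algebra are certain. The consequence rests on the ordinary meaning of 0 PN, a denominator unaffected by the shift, and an analyst who follows the endpoint section; the sizes also rest on the assumed gain and splits. The scope is one secondary endpoint in one stratum, with no effect on the primary outcome or the sample size. It should be fixed, but it does not threaten the trial's main conclusion.

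**What to change.** Before unblinding, which section 5.2 places after database lock:

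1. Delete *0 PN or* from the definition in the Secondary Objectives and in 5.1.2, so that all three definitions use the ≥2 PN numerator of 5.3. The sponsor should confirm that this is what was intended.
2. State the denominator once: oocytes inseminated for IVF, oocytes injected for ICSI.
3. Refer to this single definition in section 7.
4. Optionally, because 5.1.2 itself treats 3 PN as abnormal fertilization while both numerators count it, also report the rate with 3 PN excluded.

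The cost is one short phrase deleted in two places, one sentence and one cross-reference. The main change should need no new data, since 5.3 says the laboratories already report the rate; it is worth checking that they use the ≥2 PN numerator. The optional rate uses the 3 PN record that 5.1.2 already requires.

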5.1.3 Other study parameters

Baseline parameters are age, length, weight, ethnicity, alcohol/drugs/nicotine use, use of vitamins/steroids or other supplements, diet specifics (normal, vegetarian, vegan, gluten-free, dairy free, other), medication use, activities that cause increased scrotal temperature such as often visiting a sauna, taking a hot bath or race cycling, general health, operations or trauma in genital area, exposure to toxins in environment, conception of previous children, duration of infertility and type of diagnosis of infertility. Furthermore the age and parity of the female partner has to be documented, as well as the occurrence of endometriosis or anovulation.

Furthermore, when IVF/ICSI is performed, the amount of embryos transferred will be reported, either a single-embryo transfer (SET) or double-embryo transfer (DET).

5.2 Randomisation, blinding and treatment allocation

RANDOMISATION AND TREATMENT ALLOCATION: All couples visiting a fertility specialist for the first time or for evaluation of fertility treatment will be informed on this study. Prior to or at their actual appointment they will receive the patient information (PIF). Randomisation will be performed, after signed informed consent has been obtained, using a web-based application (Castor). We will use permuted block-design, stratified for fertility treatment (1st) and recruiting centre (2nd). Block sizes are flexible. Participants will be randomised in a 1:1 ratio to study medication (Impryl®) or placebo. Assignment to medication, using the randomisation list, will either performed at the local centre or at Radboudumc by an independent person. This person is neither participating in clinical treatment nor processing the study data. Randomisation outcome is either A (Impryl®) or B (placebo).

CODING: coding starts immediately after informed consent has been obtained. In Castor each patient will receive a combination of one letter and 3 numbers. The code will be assigned as followed: Radboudumc (A), Slingeland (B), Canisius-Wilhelmina (C), Jeroen Bosch (D), Elisabeth-TweeSteden (E), Maasziekenhuis Pantein (F), Bernhoven (G), Maxima Medisch Centrum (H), Maastricht UMC+ (I), Gelre ziekenhuizen (J), Nij Geertgen (K) Rijnstate (L), Medisch Centrum Kinderwens (M), Nij Barrahûs (N),Fertiliteitscentrum Voorburg (O), Catharina Ziekenhuis Eindhoven (P) and Bravis Ziekenhuis (Q). For example, the first patient included in Radboudumc will receive the code A001. The code will not provide any information about the received intervention (Impryl® or placebo). The list of codes corresponding with patient information and received medication will be saved in an

separate file, locked (either digital with password or a locked cabinet), only accessible for the independent person who did the randomisation.

BLINDING: The study is double blinded. All personnel, the researchers and patients will remain blinded to the intervention being received, except the personnel performing randomisation and distributing the study medication.

DEBLINDING: The indications for breaking the randomisation code are: SAE, SAR and SUSAR, as instructed by METC, or in a dire emergency, as directed by the principal investigators or trial manager. Every site has access to a deblinding form (“Formulier verbreken randomisatie code”) in which patients details, reason for deblinding, statement of principal site investigator, date and time of intervention stop and randomisation allocation will be reported. The principal site investigator will inform the coordinating investigator about the deblinding.

DISTRIBUTION: In Radboudumc and at the local study sites the person distributing the study medication is an unblinded employee of the department of Reproductive medicine or Gynaecology who is not involved in the treatment of the patient nor involved in the data collecting of the research. Every study site can decide to perform randomisation and distribution of medication at local site or at Radboudumc. On every distributing study site there will be a batch of study medication stored at room temperature, no special precautions. An unblinded authorized employee of the department of Reproductive medicine (or Gynaecology) will distribute the study medication after randomisation has been performed by Castor. The flag label (identification A = Impryl® or B = placebo) will be removed from the box and the randomisation number noted (handwritten) on the medication box. Thereafter, the box will be handed over to the patient. On the patient identification & drug accountability log (either digital or on paper) the following details will be reported: date of issue, study (randomisation) number, batch number, expiration date, amount dispensed, current storage amount, randomizer/distributor initials, hospital number, patient name and initials, date of birth and monitoring check.

All unblinded personnel performing randomisation will be trained by a site initiation to perform randomisation in Castor EDC and distribution of medication. A log list of all personnel involved in the study, with blinding status, responsibilities and signature, will be saved.

Unblinding will be performed when the study has ended, database is locked and protocol violators have been defined.

